#### C.1.3. Analysis of Continuous Secondary Endpoint

The secondary efficacy endpoint is the change in average Hb value between Baseline and the secondary efficacy period (SEP), Weeks 40 to 52. Analyses of the other efficacy endpoints are described in [Appendix D](#).

The analysis of this secondary continuous endpoint will be similar to the analysis approach for the primary efficacy shown in [Exhibit B 2](#) and [Exhibit C 1](#), except the outcome of interest in the model statement DELT\_HB3 will be replaced with DELT\_HB4, the change in Hb from baseline to the SEP. This is computed as the average Hb measure computed from the Week 40 to 52 visits minus HB\_BL.

The assessment of noninferiority will be tested using the same approach with the lower limit of the confidence interval compared to -0.75 g/dL.

Statistical Analysis Plan AKB-6548-CI-0014 and AKB-6548-CI-0015

Note that of all the continuous efficacy endpoints, only the primary efficacy endpoint and the secondary efficacy endpoint of the change in Hb between baseline and the SEP will be formally tested. All other continuous endpoint analyses will be descriptive.

#### **C.1.4. Analysis of Additional Continuous Endpoints**

The analysis of additional continuous endpoints will be similar to the analysis approach for the primary efficacy analysis (see either [Exhibit C 1](#) or [Exhibit B 2](#)) depending on whether using multiple imputation), and adjustments to these analyses approaches are outlined for each example. The team may consider alternative methods or links to analyze the certain endpoints as noted below. Several additional continuous endpoints are to be evaluated:

- Change in average Hb value between Baseline and the combined PEP and SEP (Weeks 24 to 52).
- Average weekly dose of elemental iron administered. This model will include the average weekly dose of elemental iron by route groups (oral, IV) for each analysis time period in Year 1 and Weeks 52 to EOS. Note that some variants will not be multiply imputed, in which case the analysis will be a single ANCOVA of the observed values.
- Change in hepcidin, ferritin, TSAT, serum iron, and TIBC over time. The code for this analysis is identical to that for the primary analysis with the new outcome measure of interest. Four outcomes will be tested for each lab value – the change from baseline to PEP, the change from baseline to SEP, the percentage change from baseline to PEP, and the percentage change from baseline to SEP.

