## 5.2 Definition of Baseline

In general, the baseline value will also be the value of assessment closest to the end of the window, i.e., Day 1 (first dose date). The baseline value must be assessed prior to initiation of study treatment. In contrast, the baseline value for laboratory-based efficacy outcomes (e.g., Hb, ferritin, hepcidin, TSAT, serum iron, TIBC, and lipids) will be an average of the last 1 or 2 values prior to or on the first dose date, as specified in [Section 9.1.1](#).

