### 9.1.4 Analysis of Change From Baseline in Hb to the Primary Efficacy Period

The primary analysis will be performed in the randomized population, as defined in [Section 3.1](#), to address an estimand of treatment policy in accordance with the Intention to Treat philosophy. In this open-label study, the research question is to compare the assignment of a standard of care, darbepoetin, to the investigational new drug, vadadustat, regardless of intercurrent events. This analysis includes individuals who never receive treatment, discontinue treatment, are rescued with any therapy, or withdraw consent.

The primary analysis will use multiple imputation with ANCOVA as the substantive model. Missing primary endpoint data will be imputed with the group to which the subject was randomized as described in [Appendix B](#). An ANCOVA model, as described in detail in [Appendix C](#), will be used to compare the mean change from baseline in Hb between the 2 groups.

The primary analysis model will contain treatment group, baseline Hb level, and the 2 stratification factors (region and NYHA CHF class) as predictor variables. The stratification factor of entry Hb level will not be included in the model because of the inclusion of baseline Hb. The stratification factor assignments at randomization will be respected in the analysis.

The random seeds for all the multiple imputation runs for each trial will be generated from a single master seed. The master seeds will be 10014 for CI-0014, and 10015 for CI-0015. The generation code, resulting random seeds, and corresponding analysis assignments are listed in [Appendix B](#).

The data will have shown noninferiority of vadadustat if the lower bound of the 95% confidence interval for the difference in estimated change from baseline in the 2 groups (vadadustat minus darbepoetin) exceeds the noninferiority margin of -0.75. This ensures a 1-sided alpha of 0.025 for the primary analysis. If the lower limit of the 2-sided 95% confidence interval for the difference between the mean in the vadadustat group and the mean in the darbepoetin alfa group is above zero, superiority will have been established and the finding will be interpreted as providing evidence of a greater change from baseline in Hb for vadadustat relative to the control arm.

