## Statistical Analysis Plan AKB-6548-CI-0014 and AKB-6548-CI-0015

| Endpoint   | Approach to Analysis  | Comments   |
|--|---|--|
| Hepcidin, Ferritin, TIBC   | Four outcomes – change from baseline to PEP, change from baseline to SEP, percentage change from baseline to PEP, and percentage change from baseline to SEP.

Analysis of covariance stratified by baseline strata for change from baseline to PEP or SEP. | This analysis will use only observed data  |
| Serum Iron   |   |  |
| TSAT   |   |  |
| Other laboratory endpoints ( Section 6.3.4 )                                 |   |  |
| Change from baseline in serum glucose and lipid parameters at PEP and SEP                    | ANCOVA stratified by baseline strata.   | No imputation.   |
| RBC transfusion endpoints ( Section 6.3.7 )                                  |   |  |
| Receipt of any RBC transfusion   | Mantel-Haenszel test stratified by the baseline strata  |  |
| Total number of RBC transfusions received (entire length of study)                           | See Appendix D .  | If the distribution is highly skewed either because of a large spike at zero or a long tail to the right (or both), other methods may be considered. |
| Dose adjustment ( Section 6.3.5 )  |   |  |
| Dose adjustments (entire length of study)  | Descriptive statistics  | Other methods may be considered.   |
| ESA and Rescue endpoints ( Section 6.3.8 and Section 6.3.9 ) |   |  |
| Receipt of any ESA rescue medication   | Mantel-Haenszel test stratified by the baseline strata  |  |
| Receipt of any rescue therapy (series of definitions from narrow to broad)                   | Mantel-Haenszel test stratified by the baseline strata  |  |

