### C.1. Analyses using ANCOVA

#### C.1.1. Primary Analysis

The primary analysis is based on the change in average Hb between the baseline and the primary efficacy period (PEP), Weeks 24 to 36. The noninferiority analysis will be based on a margin of -0.75 g/dL applied to the mean change in vadadustat minus darbepoetin alfa. To establish noninferiority, the lower limit of the confidence interval of the mean change in vadadustat minus darbepoetin alfa must be -0.75 g/dL or higher. If the lower limit of the 2-sided 95% confidence interval for the difference between the mean in the vadadustat group and the mean in the darbepoetin alfa group is above zero, superiority will have been established and the finding will be interpreted as providing evidence of a greater change from baseline in Hb for vadadustat relative to the control arm.

The primary efficacy analysis is based on the estimated confidence interval estimated from an ANCOVA model. The computation of this confidence interval is described in this section. Modifications for additional continuous endpoints are outlined in a separate section.

The ANCOVA model will be fit using PROC GENMOD in SAS with the following variables:

- HB\_BL – this is the average of the last 2 Hb measure on or prior to the first dose date
- DELT\_HB3 – this is computed as the average Hb measure computed from the PEP (Week 24 to 36) visits minus HB\_BL
- TRT – denotes treatment group; vadadustat or darbepoetin alfa
- STRAT1 – stratification factor of geographic region (US, EU, versus Rest of World)
- STRAT2 – NYHA CHF class 0 or I versus II or III

The basic SAS code to fit the model is in [Exhibit C 1](#), but the full process includes multiple imputed datasets as seen in [Exhibit B 2](#).

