### Exhibit C 1. SAS Code for Primary Analysis

---

```
proc genmod data=&OUTDAT2.;
    class TRT (ref="DARB") STRAT1 STRAT2 ;
    model DELT_HB3=HB_BL STRAT1 STRAT2 TRT
        / alpha=0.05 cl diagnostics residuals ;
    estimate "Primary Efficacy" TRT 1 -1;
    lsmeans TRT / cl pdiff cov;
    ods output diffs = MI_ESTIMATES lsmeans=MI_ESTIMATES2;

run;
```

---

The confidence limits for the coefficient associated with TRT in the above model are used to compute the confidence intervals based on M imputed datasets.

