#### E.1.3 Urine Albumin-to-creatinine Ratio (uACR)

A random urine spot sample is collected at the investigative site during the Baseline, Weeks 28, 52, 104, 156, 208 and end of treatment (EOT) to assess the urine albumin-to-creatinine ratio (uACR). A by-subject listing of change and percentage change from baseline in uACR will be provided, as well as geometric means (logarithmic scale) over time. The number and percent of subjects with a percent change in uACR exceeding 30% (in either direction) will be presented.

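### The ANCOVAs for the five iron parameters in SAP C.1.4 reuse the primary code, so they adjust for baseline hemoglobin and omit the parameter's own baseline, at a cost in precision

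*SAP*

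**What the plan says.** SAP C.1.4 covers change over time in hepcidin, ferritin, TSAT, serum iron and TIBC, and says: "The code for this analysis is identical to that for the primary analysis with the new outcome measure of interest". The outcomes for each parameter are "the change from baseline to PEP, the change from baseline to SEP, the percentage change from baseline to PEP", and percentage change to the SEP.

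The primary code, in Exhibit C 1 and again in Exhibit B 2, has the line "model DELT_HB3=HB_BL STRAT1 STRAT2 TRT". SAP C.1.1 defines HB_BL: "this is the average of the last 2 Hb measure on or prior to the first dose date". STRAT1 is region and STRAT2 is NYHA class. Section 9.1.4 gives the same model in words: "The primary analysis model will contain treatment group, baseline Hb level, and the 2 stratification factors".

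For these parameters Table 3 says "Analysis of covariance stratified by baseline strata for change from baseline to PEP or SEP", on observed data only. It names no baseline covariate.

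Section 5.2 does define the missing covariate: "the baseline value for laboratory-based efficacy outcomes (e.g., Hb, ferritin, hepcidin, TSAT, serum iron, TIBC, and lipids) will be an average" of the last one or two values up to first dose.

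On status, Section 9.3 calls the other efficacy endpoints exploratory and applies no multiplicity correction. C.1.3 says that every continuous endpoint apart from the two Hb changes is descriptive. C.1.4 nevertheless speaks of testing four outcomes per laboratory value.

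**The concern.** An ANCOVA of change normally carries the baseline of the variable being analysed, because that is usually the strongest predictor of the change. The primary model does this: the outcome is change in Hb and the covariate is baseline Hb. If only the outcome is swapped, the covariate no longer matches it.

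The omission reads like a carry-over from the Hb model. Baseline hepcidin, ferritin, TIBC and TSAT are already predictors in the imputation model (Table B 1). In Appendix D.3 the covariate is matched to the endpoint, with baseline Hb for Hb-related events and baseline eGFR for CKD progression.

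What is at stake is the precision of the iron-metabolism comparison. Protocol Section 4.3 presents effects on iron as a potential benefit of vadadustat, so readers will use these estimates and intervals even though no formal claim rests on them.

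**Working it through.** **1. The model as written.** Substituting the outcome into the Exhibit C 1 line gives: change (or percentage change) in the iron parameter = HB_BL, STRAT1, STRAT2, TRT. The parameter's own baseline is absent.

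**2. Whether other text repairs it.**
- Table 3 adds no covariate.
- C.1.4 allows alternative methods for endpoints where it notes them, and notes none for these parameters.
- The skewness fallback in Table 3 covers iron dose and RBC transfusion counts, not these laboratory values.

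**3. Cost in precision for absolute change.** The documents give no SD, effect or power for these parameters, so there is no planned figure to reproduce. Let the baseline and period values have equal SD s and correlation rho, and let baseline Hb be nearly unrelated to the parameter.
- Variance of change without own baseline: 2(1−rho)s².
- Residual variance with own baseline: (1−rho²)s².
- Ratio, adjusted over written: (1−rho²)/[2(1−rho)] = (1+rho)/2.

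| rho | Variance ratio | Interval-width ratio (square root) | 925 per arm as written is worth, with own baseline |
|---|---|---|---|
| 0.14 | 0.57 | 0.75 | 925 × 0.57 = 527 |
| 0.4 | 0.70 | 0.84 | 925 × 0.70 = 648 |
| 0.58 | 0.79 | 0.89 | 925 × 0.79 = 731 |
| 0.6 | 0.80 | 0.89 | 925 × 0.80 = 740 |
| 0.8 | 0.90 | 0.95 | 925 × 0.90 = 833 |

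The 925 per arm is from SAP 2.6. The range 0.14 to 0.58 is from SAP A.3.1, where it describes Hb in other trials. Using it for iron parameters is an assumption, and so are the other values of rho.

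**4. If the SDs differ.** With a follow-up SD of k times the baseline SD, the two variances are (1+k²−2·rho·k)s² and k²(1−rho²)s². Their difference is (1−rho·k)²s², which is never negative. The size of the gain changes with k, but own-baseline adjustment does not lose precision apart from one degree of freedom.

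**5. Choice of scale.** This is a simulation on assumed values: lognormal baseline and follow-up, 925 per arm, true ratio 0.90, correlation −0.2 between Hb and the log parameter at baseline, no missing data, strata omitted, 1000 runs per row. Entries are the percentage of runs significant at the two-sided 5% level.

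| Log SD | rho | Raw change, Hb baseline | Percent change, Hb baseline | Raw change, own baseline | Log ratio, own log baseline |
|---|---|---|---|---|---|
| 0.3 | 0.3, 0.5 or 0.7 | 100 | 100 | 100 | 100 |
| 0.7 | 0.3 | 61.6 | 62.8 | 83.6 | 92.5 |
| 0.7 | 0.5 | 72.7 | 80.6 | 88.8 | 95.8 |
| 0.7 | 0.7 | 89.1 | 96.9 | 95.0 | 99.5 |
| 1.0 | 0.3 | 24.4 | 26.8 | 42.4 | 64.3 |
| 1.0 | 0.5 | 34.1 | 40.9 | 49.1 | 76.1 |
| 1.0 | 0.7 | 46.1 | 70.8 | 59.9 | 88.1 |

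The gain from a log-ratio analysis runs from none at log SD 0.3 to large at 0.7 to 1.0. The documents do not say where these parameters lie.

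**The case against.** The strongest reply is that little depends on these models. No iron parameter is a primary or key secondary endpoint, the analyses are exploratory and descriptive, and power is a weak yardstick for them. That stands and sets the severity. It does not make the covariate right, and the correction is free.

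A reader might draw stronger conclusions, which the documents do not support.

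- **That the values are skewed and the scale is therefore wrong.** Nothing in the SAP or protocol says that any of the five is skewed. What can be said is that no log-scale analysis or skewness fallback is specified for them. For uACR, Appendix E.1.3 plans change and percentage change "as well as geometric means (logarithmic scale) over time", but that is a safety summary. It contains no log-scale treatment model for the iron analyses to contradict.
- **That regression to the mean biases the comparison.** Under 1:1 randomization it acts on both arms alike in expectation. What remains is chance imbalance and a wider interval.
- **That the glucose and lipid analyses share the defect.** The identical-code sentence names only the five iron parameters. Table 3 is silent on covariates for glucose and lipids, but equally silent for the combined PEP and SEP change in Hb. Its silence shows a gap in wording, not an omitted covariate.
- **That percentage change should be dropped or HB_BL replaced.** Both are preferences. In the simulation, percentage change did at least as well as raw change with the same Hb covariate. Section 9.1.4 leaves out the entry-Hb stratum because baseline Hb is in the model, which is a reason to keep HB_BL.

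**Conclusion.** The point holds in limited form. Followed as written, C.1.4 fits the five iron parameters without their own baseline, and no other text restores it. For absolute change, the variance with own-baseline adjustment would be 0.57 to 0.90 of that from the written model for rho from 0.14 to 0.8, so intervals would be about 5% to 25% narrower. This rests on equal SDs before and after treatment, little correlation between baseline Hb and the parameter, and correlations that the documents do not give for these parameters.

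The absence of systematic bias assumes complete data. Table 3 uses observed values only, so if missingness depended on the parameter's own baseline, conditioning on that baseline would also help there. This was not quantified.

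The log-scale suggestion is a supplement whose value depends on undocumented skewness. Severity is low, and the primary and key secondary Hb conclusions are untouched.

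**What to change.** - **C.1.4 and the matching Table 3 rows:** state that the primary code is used with the outcome replaced and the parameter's own baseline, as defined in Section 5.2, added as a covariate for each of the five iron parameters. HB_BL may stay.
- **Table 3, glucose and lipids:** name the parameter's own baseline as covariate.
- **Optional supplement:** for any of these parameters found right-skewed on blinded review, prespecify log(post/baseline) with log baseline as covariate, reported as a geometric mean ratio.

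The cost is a few lines of SAP wording and one term in the model statement, before database lock and unblinding. No new data are needed.

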#### **C.2. Analyses Using MMRM**

Additional sensitivity analyses will be performed under an alternate framework to assess the robustness of the primary efficacy analysis with respect to missing data.

A mixed model repeated measures (MMRM) will be fit to the observed data only *without imputing missing values*. The repeated measures will be the observed averages for analysis time periods 1, 2, and 3 (See definitions, [Section 5.1](#)). Note that analysis time period 4 will be included in the sensitivity analysis for the continuous secondary efficacy endpoint ([Section 9.2](#)).

The following variables will be used in the model:

- DELT\_HB – this is computed as the Hb measure minus HB\_BL
- ASPER – refers to the subperiod number post-baseline (1, 2, 3)
- SUBJID – denotes subject identifier

Statistical Analysis Plan AKB-6548-CI-0014 and AKB-6548-CI-0015

The SAS code to fit the model is as follows:

### **Exhibit C 2. SAS Code for Sensitivity Analysis for the Primary Efficacy Endpoint**

---

```
proc mixed data = &LONGDAT. method=reml alpha=0.05 covtest;
  where ASPER le 3;
  class SUBJID TRT (ref="DARB") ASPER (ref=last)
STRAT1 STRAT2 ;
  model DELT_HB3 = HB_BL STRAT1 STRAT2 TRT ASPER
    HB_BL*ASPER TRT * ASPER / s ddfm=kr
  repeated ASPER / subject = SUBJID type = UN r;
  estimate "MMRM Sensitivity" TRT 1 -1 TRT*ASPER 0 0 1 0 0 -1/ cl;
  ods output estimates=MMRM_EST;
run;
```

---

The test of efficacy is obtained from the ESTIMATE statement. The model will have the following characteristics:

- The response variable will be the vector of observed change (average of per-window changes) in the primary efficacy endpoint from baseline to the average value in each analysis time period. The endpoint will consist of the three repeated measures defined as Analysis Time Period X Hb – baseline Hb.
- Repeated post-baseline measurements from each subject will be identified by the subject identifier denoted as SUBJID in the PROC MIXED code.
- Within-subject correlations will be modeled using an unstructured covariance structure.
- In the unlikely situation that this model does not converge, the model will use the heterogeneous Toeplitz structure, which assumes the correlation between 2 repeated measurements depends solely on their lag in visit number and that the variance of the endpoint may differ over time.
- If the model still does not converge with the heterogeneous Toeplitz structure, the model will use a homogeneous Toeplitz structure.
- Finally, if the model using the homogeneous Toeplitz structure does not converge, the model will use a compound symmetry structure which assumes equal correlation for a subject's measurements, regardless of how far apart in time they were taken.
- The Kenward-Roger degrees of freedom approximation will be used in calculating the ESTIMATE contrasts for the sensitivity analysis.

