### Exhibit B 2. SAS Code to Compute the M Estimates of Treatment Effect

---

```

*** derive primary and other endpoints;
data &OUTDAT2.;
  set &OUTDAT.;
  DELT_HB3 = HB_3 - HBBL;
  DELT_HB4 = HB_4 - HBBL;
  if (STRAT3 eq "US" and 10 le DELT_HB3 le 11) or
    (STRAT3 ne "US" and 10 le DELT_HB3 le 12) then
    HBRNGS3="Yes";
  else HBRNGS3="No";
  if (STRAT3 eq "US" and 10 le DELT_HB4 le 11) or
    (STRAT3 ne "US" and 10 le DELT_HB4 le 12) then

```

---

---

```

        HBRNGS4="Yes";
    else HBRNGS4="No";
run;
proc genmod data=&OUTDAT2.;
    by _IMPUTATION_
    class TRT (ref="DARB") STRAT1 STRAT2 ;
    model DELT_HB3=HB_BL STRAT1 STRAT2 TRT
        / alpha=0.05 cl diagnostics residuals ;
    estimate "Primary Efficacy" TRT 1 -1;
    lsmeans TRT / cl pdiff cov;
    ods output diffs = MI_ESTIMATES lsmeans=MI_ESTIMATES2;
run;

```

---

The execution of the above set of SAS code will provide the datasets MI\_ESTIMATES and MI\_ESTIMATES2 which will contain M lines of data that include the estimates and standard errors for each imputed dataset. The final result is then obtained with application of PROC MIANALYZE provided in [Exhibit B 3](#).

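### The printed MMRM sensitivity code names the primary-period change as its response, contradicts the SAP text, and should be corrected before it is run

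*SAP*

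**What the plan says.** SAP Section 9.1.5 lists a mixed model for repeated measures, fitted to observed data without imputation, among the sensitivity analyses of the primary endpoint. Appendix C.2 gives its purpose: "to assess the robustness of the primary efficacy analysis with respect to missing data". It also gives the data: "The repeated measures will be the observed averages for analysis time periods 1, 2, and 3". The C.2 variable list names the response DELT_HB, of which it says "this is computed as the Hb measure minus" baseline Hb. The bullets under the exhibit agree: "The endpoint will consist of the three repeated measures defined as Analysis Time Period X Hb" minus baseline.

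The code in Exhibit C 2 names a different response: "model DELT_HB3 = HB_BL STRAT1 STRAT2 TRT ASPER". The covariance is unstructured within subject: "repeated ASPER / subject = SUBJID type = UN r". If the model does not converge, the SAP steps down to heterogeneous Toeplitz, then homogeneous Toeplitz, then compound symmetry.

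DELT_HB3 is defined elsewhere as a single value per subject. Appendix C.1.1 says of it: "this is computed as the average Hb measure computed from the PEP (Week 24 to 36) visits minus" baseline. Exhibit B 2 derives it as "DELT_HB3 = HB_3 - HBBL". The input dataset of Exhibit C 2, `&LONGDAT.`, is not defined anywhere.

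Section 9.2 extends the same MMRM to four post-baseline periods for the secondary endpoint.

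**The concern.** An MMRM helps with missing data because a subject with no haemoglobin in Weeks 24–36 still contributes through periods 1 and 2, by way of the within-subject covariance. That requires a response that takes its own value in each period. DELT_HB3 does not: it exists only for subjects with a primary-period value, and there is one value per subject.

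Such subjects are likely to exist. SAP Section 2.2 says that no laboratory assessments are planned after permanent discontinuation of study drug, so someone who stops before Week 24 may have period 1 and 2 values and nothing later. Of the analyses in Section 9.1.5, the MMRM is the one that uses those early values without relying on the imputation model. Running it on the wrong variable would lose that property, and one of the possible outcomes is a plausible-looking estimate.

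**Working it through.** **1. Text against code.** The exhibit states no numerical result to reproduce, so the first check sets the passages side by side.

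| Place | Response |
|---|---|
| Section 9.1.5; Appendix C.2 text | Observed averages, periods 1, 2, 3 |
| C.2 variable list | DELT_HB (Hb minus baseline) |
| Bullet under Exhibit C 2 | Three period-specific changes |
| MODEL statement, Exhibit C 2 | DELT_HB3 |
| Appendix C.1.1; Exhibit B 2 | DELT_HB3 = period 3 minus baseline |

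Only the MODEL statement departs from the rest.

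**2. What the printed code would do.** This depends on how `&LONGDAT.` is built.

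*(a) DELT_HB3 copied to all three rows.* The three residuals of a subject are identical. In a simulated set of 1000 subjects the 3×3 residual covariance had every entry equal to 2.223, so its rank is 1. Under compound symmetry with variance σ² and correlation ρ, a subject with residual r contributes to −2 log-likelihood (constant omitted)

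3 ln σ² + 2 ln(1−ρ) + ln(1+2ρ) + 3r²/[σ²(1+2ρ)].

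The last term stays bounded while 2 ln(1−ρ) falls without limit as ρ approaches 1:

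| ρ | −2 log-likelihood |
|---|---|
| 0.5 | 3200.8 |
| 0.99 | −4717.7 |
| 0.9999 | −13928.1 |
| 0.99999999 | −32348.8 |

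Compound symmetry is a special case of both Toeplitz structures and of the unstructured form, so the likelihood is unbounded under all four. The listed fallbacks cannot rescue the fit.

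*(b) DELT_HB3 present only on the period-3 row.* Rows for periods 1 and 2 have no response. Subjects without a primary-period Hb drop out, and the treatment estimate is that of a complete-case ANCOVA.

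*(c) DELT_HB3 not in the dataset,* for example because it holds DELT_HB as C.2 lists. The step stops with an error.

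**3. Size under outcome (b).** From the SAP: 925 per arm and SD 1.5 g/dL (Sections 2.6 and 2.7). Assumed: correlations between periods 1–2, 1–3 and 2–3 of 0.7, 0.5 and 0.7; true difference 0; darbepoetin missingness at random; vadadustat missingness more likely when the period-2 change was low, on a logit slope of 0.3, 0.6 or 1.0 per g/dL. Strata were omitted, and there were 400 replicates per row. The correct MMRM was computed by maximum likelihood in factored form: the treatment coefficient for period 3 given periods 1 and 2 among subjects observed in period 3, plus the coefficients on periods 1 and 2 times the treatment effects in those periods.

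| Missing, vadadustat | Missing, darbepoetin | MMRM, correct response | Complete case |
|---|---|---|---|
| 5.4% | 5% | −0.002 | +0.023 |
| 6.9% | 5% | −0.009 | +0.052 |
| 10.2% | 5% | 0.000 | +0.129 |
| 10.7% | 10% | −0.002 | +0.048 |
| 12.9% | 10% | 0.000 | +0.112 |
| 17.0% | 10% | +0.002 | +0.207 |
| 20.9% | 20% | +0.002 | +0.098 |
| 23.3% | 20% | −0.005 | +0.188 |
| 27.1% | 20% | +0.001 | +0.313 |

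Positive values favour vadadustat, the anti-conservative direction for noninferiority. Against the margin of 0.75 g/dL, the extremes are 0.023/0.75 = 3% and 0.313/0.75 = 42%.

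**The case against.** The strongest reply is that this is a wrong variable name and not a wrong plan. The intended response is stated in Section 9.1.5, in the C.2 text, in the variable list and directly beneath the code, and the opening of Appendix C calls its code examples. A competent programmer would see the conflict. This largely stands: a reader might infer that the SAP plans a complete-case analysis labelled as an MMRM, and the text rules that out. It does not remove the need for correction, because the SAP Introduction says that its wording and its code together fix the intent of each analysis. Here they disagree, and nothing says which prevails.

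A reader might also infer that the error would silently confirm the primary result. That needs outcome (b). Outcomes (a) and (c) fail visibly, and the documents do not say which layout applies. A singular covariance and quiet agreement with a complete-case result cannot both occur, since they need different datasets.

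Little rests on this analysis alone. The primary multiple imputation already uses period 1 and 2 haemoglobin (Exhibit B 1), and the tipping point analysis probes departures from missing at random. Protocol Section 11.5 expects minimal missing data. With 925 per arm and SD 1.5 the unadjusted standard error is 1.5 × √(2/925) = 0.07 g/dL, so when the true difference is near zero a bias of the sizes shown would not change a noninferiority conclusion. All of this stands and limits the consequence.

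The exhibit also appears to lack a semicolon after `ddfm=kr`. That may have been lost when the PDF was read, and it is not counted here.

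**Conclusion.** The MODEL statement in Exhibit C 2 is wrong as printed and contradicts the SAP's own text. The finding that it names a period-3-only variable rests on the documents alone. What would happen if it were run is conditional on `&LONGDAT.`: an unbounded likelihood, a complete-case ANCOVA, or an error.

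The range of +0.02 to +0.31 g/dL applies only to the complete-case outcome, and only if missingness depends on earlier haemoglobin mainly in the vadadustat arm. It illustrates direction and possible scale and does not predict this trial's result.

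The consequence is confined to the MMRM sensitivity analysis and its extension to the secondary endpoint. The documents do not support a wider reading, that the primary noninferiority result or the handling of missing data as a whole is compromised. The correction is still worth making before unblinding, since changing a prespecified model afterwards invites questions.

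**What to change.** In Exhibit C 2, replace DELT_HB3 with DELT_HB in the MODEL statement. Define `&LONGDAT.` in one sentence as one record per subject per analysis period, with DELT_HB equal to that period's average Hb minus baseline Hb. Apply the covariance fallback sequence only to the corrected model.

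For the secondary endpoint, state that the same response is used with periods 1 to 4, and adapt the WHERE and ESTIMATE lines so that the contrast falls on period 4. Substituting DELT_HB4, by analogy with Appendix C.1.3, would repeat the error.

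The cost is one variable name, one definition and a four-period version of the exhibit. No new data are needed, and the primary analysis does not change. Because the SAP is shared, the correction covers both CI-0014 and CI-0015.
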